## 10.3 Statistical Analyses

The Statistical Analysis Plan will be developed and finalized before database lock, and below is a summary of planned statistical analyses of the primary and secondary endpoints.

A description of the participant population will be included in a statistical output report, including subgroups of age, gender, and race.

### 10.3.1 Efficacy Analyses

The primary efficacy analyses (Table 10.3.1-1) will be performed on the treated population for the final analysis. Efficacy analyses based on the treated population may be performed for interim analyses when the minimum follow-up period is less than sufficient to warrant adequate interpretation of the result. Details of the censoring scheme on time-to-event endpoints such as DOR, PFS, TTR, and OSR will be described in the Statistical Analysis Plan.

Analysis of exploratory endpoints using iRECIST by BICR (ORR, DOR, and PFS) will also be performed.

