**Table 4-1: Objectives and Endpoints**

Objectives	Endpoints

 
To measure [REDACTED], and assess [REDACTED] change over time and in association with response
 
	
 
Mean EQ-5D-5L utility index scores and EQ-5D-VAS scores and change from baseline scores
 
Summary measures of [REDACTED] and correlation/ measure of association of anti-tumor activity and change (or % change) from baseline in [REDACTED]
 

For Part 2C Primary 
 
To compare the efficacy of BMS-986288 in combination with nivolumab vs regorafenib in the 3L/4L MSS CRC setting.
 
	
 
ORR per RECIST v1.1 by BICR
 

For Part 2C Secondary 
 
To compare the efficacy of BMS-986288 in combination with nivolumab vs regorafenib in the 3L/4L MSS CRC setting
 
To characterize the safety and tolerability of BMS-986288 in combination with nivolumab vs regorafenib in the 3L/4L MSS CRC setting
 
	
 
DOR and PFS per RECIST v1.1 by BICR, and OS
 
ORR, DOR, and PFS per RECIST v1.1 by Investigator assessment
 
Incidence of AEs, SAEs, AEs meeting protocol-defined DLT criteria, AEs leading to discontinuation, and death
 

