## **Part 2C**

Part 2C is a randomized, open-label study with 2 treatment arms, nivolumab in combination with BMS-986288 (Arm C) versus regorafenib (Arm D). Once enrolled in IRT, participants who have met all eligibility criteria for Part 2C will be randomized in a 2:1 ratio to nivolumab in combination with BMS-986288 (Arm C) or regorafenib (Arm D) and stratified by liver metastases status. Participants in Part 2C Arm D receiving regorafenib will have the option to transition to BMS-986288 in combination with nivolumab (Part 2C Arm Z) after BICR-assessed progression.

An additional dose of BMS-986288 █ mg or █ mg) in combination with nivolumab may be opened in Part 2C (as Arm E). This additional dose level will not be randomized with Arm C and Arm D.

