At the final analysis, there will be approximately [REDACTED] randomized participants in each experimental arm and [REDACTED] participants in the [REDACTED] arm ([REDACTED] participants from the randomized control arm and [REDACTED] participants from the [REDACTED] control data). This will provide approximately 80% power to detect the delta ORR of [REDACTED] with a two-sided alpha of 0.1. The trial can reach statistical significance when the delta ORR is [REDACTED] or larger. If it is not possible to borrow information from [REDACTED] data or studies, approximately [REDACTED] randomized participants in the experimental arm and [REDACTED] participants from the randomized control arm will be evaluated. This will provide approximately 73% power to detect the delta ORR of [REDACTED] with a two-sided alpha of 0.1 and unpooled variance assumption.

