**Table 10.2-1: Populations for Analyses**

Population	Description
Enrolled	All participants who sign informed consent and are registered into the Interactive Response Technology (IRT)
Treated	All participants who take at least 1 dose of study treatment
Response-evaluable	All treated participants with measurable disease at baseline and 1 of the following: (a) at least 1 post baseline tumor assessment; (b) clinical progression; and (c) death
Pharmacokinetic	All treated participants who have evaluable concentration-time data
Immunogenicity	All treated participants who have baseline and at least 1 post-baseline pre-infusion immunogenicity assessment
Biomarker	All treated participants with available biomarker data
Clinical outcomes population (Part 2A and Part 2B only)	All treated participants who have a valid clinical outcomes assessment at baseline and at least 1 matched on-treatment post-baseline assessment

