**Table 10.3.1-1: Efficacy - Statistical Analyses**

Endpoint	Statistical Analysis Methods
ORR is defined as the proportion of all treated participants whose BOR is either CR or PR by Investigator (Part 2A/Part 2B) and BICR (Part 2C) per RECIST v1.1.  BOR for a participant will be assessed per RECIST v1.1 by Investigator (Part 2A/Part 2B) and BICR (Part 2C), unless otherwise specified.	Estimate of ORR and corresponding 2-sided exact 95% CI using the Clopper-Pearson method by treatment for each tumor type.
DOR for a participant with a BOR of CR or PR is defined as the time between the date of first response and the date of the first objectively documented tumor progression per RECIST v1.1, or death, whichever occurs first.	Estimate by the Kaplan-Meier method and corresponding 2-sided 95% CI using Brookmeyer and Crowley methodology (using log-log transformation) by treatment for each tumor type.
PFS  PFS for a participant is defined as the time from the first dosing date to the date of first objectively documented disease progression or death due to any cause, whichever occurs first.	Estimate by the Kaplan-Meier method and corresponding 2-sided 95% CI using Brookmeyer and Crowley methodology (using log-log transformation) by treatment for each tumor type.
TTR  TTR for a participant is defined as the time from the first dosing date to the date of the first confirmed response (CR or PR) per RECIST v1.1.	Listing of TTR will be provided.
OSR  OSR at a certain time point is defined as the proportion of subjects alive at that time point since the first dosing date.	Estimate by the Kaplan-Meier method and corresponding 2-sided 95% CI using Brookmeyer and Crowley methodology (using log-log transformation) by treatment for each tumor type.

Abbreviations: BICR = blinded independent central review; BOR = best overall response; CI = confidence interval; CR = complete response; DOR = duration of response; ORR = objective response rate; OSR = overall survival rate; PFS = progression-free survival; PR = partial response; RECIST = Response Evaluation Criteria in Solid Tumors; TTR = time to response.

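### Part 2C randomises Arm C against Arm D, but its final ORR counts treated participants only, its PFS starts at first dose, and OS is defined only as a rate from first dose

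*Combined protocol and SAP*

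**What the plan says.** **Design.** Section 7.2 states that "participants who have met all eligibility criteria for Part 2C will be randomized in a 2:1 ratio" to Arm C or Arm D, stratified by liver metastasis status. Section 7.3 makes the study open to sponsor, site and participant, with the arm obtained from the IRT before treatment starts. In Table 4-1 the Part 2C primary objective is a comparison with regorafenib on ORR by BICR. The secondary endpoints include "DOR and PFS per RECIST v1.1 by BICR, and OS".

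**Sizing.** Section 10.1.6 gives final-analysis power of about 80% with borrowed controls and about 73% without. It refers to "randomized participants in each experimental arm" and to participants from the randomised control arm. Section 5.2 also counts Arms C and D as randomised. The synopsis counts the same arms as treated.

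**Analysis.** Section 10.3.1 says the primary efficacy analyses "will be performed on the treated population for the final analysis". Table 10.2-1 defines Treated as "All participants who take at least 1 dose of study treatment" and has no randomised population. In Table 10.3.1-1, "ORR is defined as the proportion of all treated participants whose BOR is either CR or PR", and that row names BICR as the assessor for Part 2C. In the same table, "PFS for a participant is defined as the time from the first dosing date".

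**Survival.** Table 10.3.1-1 has an OS-rate row, "the proportion of subjects alive at that time point since the first dosing date", estimated by Kaplan-Meier. Section 10.3.7 adds that the 1-year and 2-year rates are handled like PFS. There is no row for OS as a time-to-event endpoint. A Table 2-2 footnote says that efficacy data gathered after an Arm D participant moves to the combination are analysed apart.

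**The concern.** In an open-label trial the arm is known before the first dose, so the decision not to start can depend on the arm. Removing non-starters is then an exclusion made after randomisation that may differ between arms, and the comparison loses part of the protection that randomisation gives. Section 5.4.4 adds stratification to limit imbalance between arms; dropping non-starters can undo some of it. The analysed set would also differ from the set named in the power statement.

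For survival the gap is in the definition. Arm D participants may transition to Arm Z after BICR progression. With no OS row, and a footnote that separates efficacy data after transition, two analysts could reasonably disagree on whether Arm D deaths after transition count in the OS comparison.

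**Working it through.** **1. The plan's own figures.** The 80% and 73% cannot be reproduced, because arm sizes, the ORR difference and the borrowed number are redacted. They can be checked for plausibility with power = Φ(δ/√[pE(1−pE)/nE + pC(1−pC)/nC] − 1.645), which uses unpooled variance and two-sided alpha 0.1. Assume a control ORR of 3%, δ = 10 points and 86:43 randomised. The standard error is 0.0446 and power is Φ(0.10/0.0446 − 1.645) = 72.4%. Adding 31 to 95 control participants at full weight brings power to within 2 points of 80%. The two stated powers can therefore coexist, and this point does not dispute them.

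**2. What the rules exclude.** Set side by side, Section 10.1.6 counts randomised participants, while Section 10.3.1 and the ORR row count treated participants. Someone randomised but not dosed falls outside the ORR denominator and has no PFS start date. The Enrolled set is no substitute, since it rests on consent and IRT registration and not on randomisation. Section 10.3.1 leaves censoring to the SAP, but the protocol itself fixes the population and Table 10.3.1-1 fixes the time origin.

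**3. Effect on the ORR difference.** Let p be the ORR among treated participants and f the share of randomised participants never dosed (E experimental, C control). Count undosed participants as non-responders in the randomised set.

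- Treated difference: pE − pC
- Randomised difference: pE(1−fE) − pC(1−fC)
- Treated minus randomised: pE·fE − pC·fC

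All values of p and f are assumptions. Shift in percentage points:

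| ORR, E v C | f | Controls only undosed | Both arms | Experimental only |
|---|---|---|---|---|
| 15% v 3% | 5% | −0.15 | +0.60 | +0.75 |
| 20% v 5% | 5% | −0.25 | +0.75 | +1.00 |
| 15% v 6.7% | 5% | −0.33 | +0.42 | +0.75 |
| 15% v 3% | 10% | −0.30 | +1.20 | +1.50 |
| 20% v 5% | 10% | −0.50 | +1.50 | +2.00 |
| 15% v 6.7% | 10% | −0.67 | +0.83 | +1.50 |

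The largest positive entry is 0.20 × 0.10 = 2.0 points and the most negative is −0.067 × 0.10 = −0.67 points. The shift is negative when only controls fail to start and positive in the other two patterns.

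**4. Effect on power.** Assume 80:40 randomised and treated-set ORRs of 12% v 2%. With 5% undosed in each arm, power is 74.1% in the treated set and 73.9% in the randomised set. With 2% undosed in the experimental arm and 15% in control, it is 73.6% and 78.1%. Across the scenarios run (60:30 and 80:40; 12% v 2%, 15% v 2%, 20% v 3%), all-randomised power lies between about 0.2 points below and 4.5 points above treated-set power. Loss of power is not the argument; bias is.

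**The case against.** **The effect may be small.** This stands. Section 5.1.5 requires at least 2 completed regorafenib cycles before transition, so Arm D participants have a reason to start. Even at 10% never dosed, the assumed shift is at most 2 points.

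**The documents mix their counting units.** This stands in part. The synopsis says treated, and Section 5.2 opens with participants treated before listing Part 2C as randomised. A reader should not infer that every sizing statement uses randomised participants; the power statement in Section 10.1.6 does.

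**The SAP will settle it.** Section 10.3 calls itself a summary, so detail may follow. But a SAP that analysed all randomised participants would contradict the population and denominator already written. Section 10.3.1 also permits treated-set analyses at interims, which hints that a different final set may have been intended; none is written.

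**Survival is not wholly undefined.** Correct: a rate, a method and a time origin exist. What is missing is OS as a time-to-event comparison and the handling of deaths after transition.

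**Stronger readings that the documents do not support.**

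- A reader might infer how often the two sets would give different verdicts. The plan names no comparative test, and on the same assumed inputs the maximum moves from about 8% (unpooled z) to about 12% (pooled z) and about 21% (Fisher's exact test). No such percentage is claimed.
- A reader might infer that randomised non-starters will re-enter and be counted twice. Sections 6 and 6.4.1 allow re-enrolment of people who leave untreated, but neither mentions someone already randomised.
- A reader might infer that crossover distorts the primary endpoint. Transition needs BICR progression, so BICR ORR and BICR PFS are unaffected.

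**Conclusion.** The point holds on the text. As written, the final Part 2C efficacy analysis excludes randomised participants who were never dosed, after their arm is known, and OS lacks a definition suited to a randomised comparison. This should be corrected before the final analysis.

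Confidence is high on what the plan says and low on how much it would matter. The shift of about −0.7 to +2.0 points in the ORR difference rests entirely on assumed ORRs of 15-20% v 3-6.7% and at most 10% never dosed. If nearly everyone starts treatment, the effect is close to nil. No size is claimed for PFS or OS.

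**What to change.** - **Population.** Add an all-randomised set to Table 10.2-1 for Arms C and D, by assigned arm, each participant counted once under the first randomisation. Use it for the Part 2C ORR, PFS and OS comparison in Section 10.3.1 and Table 10.3.1-1.
- **ORR.** Count undosed or unassessed participants as non-responders.
- **PFS.** Time it from randomisation. An undosed participant with no post-baseline scan and no death is censored at randomisation.
- **OS.** Add a row to Table 10.3.1-1: randomisation to death from any cause, keeping Arm D deaths after transition to Arm Z. Limit the separate-analysis wording for efficacy in the Table 2-2 footnote to Arm Z response and PFS.
- **Treated set.** Keep it for safety, as a sensitivity analysis, and for Arm E, which Section 7.2 says is not randomised with Arms C and D.
- **External control.** Use a matching population and time origin where its data allow; otherwise label the comparison as unmatched.

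Parts 1, 2A and 2B are unchanged.

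**Cost.** Mostly wording and SAP programming. ORRs may read slightly lower. The gain for PFS is small, because Table 2-2 schedules scans from first dose and most undosed participants would be censored at once. Survival contacts are needed for the few undosed participants, because Section 5.1.3.3 starts follow-up at end of treatment. Participants who transition are already followed under Section 5.1.5 for up to 2 years from last dose.

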**Table 10.3.1-1: Efficacy - Statistical Analyses**

Endpoint	Statistical Analysis Methods
ORR is defined as the proportion of all treated participants whose BOR is either CR or PR by Investigator (Part 2A/Part 2B) and BICR (Part 2C) per RECIST v1.1.  BOR for a participant will be assessed per RECIST v1.1 by Investigator (Part 2A/Part 2B) and BICR (Part 2C), unless otherwise specified.	Estimate of ORR and corresponding 2-sided exact 95% CI using the Clopper-Pearson method by treatment for each tumor type.
DOR for a participant with a BOR of CR or PR is defined as the time between the date of first response and the date of the first objectively documented tumor progression per RECIST v1.1, or death, whichever occurs first.	Estimate by the Kaplan-Meier method and corresponding 2-sided 95% CI using Brookmeyer and Crowley methodology (using log-log transformation) by treatment for each tumor type.
PFS  PFS for a participant is defined as the time from the first dosing date to the date of first objectively documented disease progression or death due to any cause, whichever occurs first.	Estimate by the Kaplan-Meier method and corresponding 2-sided 95% CI using Brookmeyer and Crowley methodology (using log-log transformation) by treatment for each tumor type.
TTR  TTR for a participant is defined as the time from the first dosing date to the date of the first confirmed response (CR or PR) per RECIST v1.1.	Listing of TTR will be provided.
OSR  OSR at a certain time point is defined as the proportion of subjects alive at that time point since the first dosing date.	Estimate by the Kaplan-Meier method and corresponding 2-sided 95% CI using Brookmeyer and Crowley methodology (using log-log transformation) by treatment for each tumor type.

Abbreviations: BICR = blinded independent central review; BOR = best overall response; CI = confidence interval; CR = complete response; DOR = duration of response; ORR = objective response rate; OSR = overall survival rate; PFS = progression-free survival; PR = partial response; RECIST = Response Evaluation Criteria in Solid Tumors; TTR = time to response.

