For Part 1, 2A, 2B Exploratory 

• To explore the potential association between anti-tumor activity and pharmacodynamic markers, such as, but not limited to, [REDACTED] prior to treatment and following administration of BMS-986288 alone and in combination with nivolumab

• To explore the associations between BMS-986288 PK, safety, efficacy, and clinical biomarkers

• To characterize the immunogenicity of BMS-986288 and nivolumab

• To assess the preliminary efficacy of BMS-986288 alone and in combination with nivolumab in select advanced solid tumors using iRECIST

• To assess the OS in participants treated with BMS-986288 alone and in combination with nivolumab

• To assess the potential effect of BMS-986288 when administered [REDACTED] on the QTc interval

• To characterize the PK and bioavailability of BMS-986288 when [REDACTED]

• To explore the impact of treatment on NSCLC participant-reported symptoms and health-related quality of life (Part 2A and Part 2B only)

• To explore participant overall perception of bother in relation to treatment-related symptomatic side effects (Part 2A and Part 2B only)

• To explore overall health status (Part 2A and Part 2B only)

	

• Summary measures of anti-tumor activity by pretreatment level of biomarkers of interest; correlation/measure of association of anti-tumor activity and change (or % change) from baseline in biomarkers of interest

• Association measures between BMS-986288 PK levels by [REDACTED], select outcomes, and biomarkers of interest

• Incidence of ADA to nivolumab and BMS-986288

• ORR, DOR, and PFS per iRECIST by BICR

• OSR at 1 year and 2 years

• Summary measures of ECG parameters and changes in QTcF (<math>\Delta</math>QTcF) from baseline

• Summary of PK parameters when BMS-986288 is [REDACTED] alone or in combination with nivolumab

• Mean NSCLC-SAQ scores and change from baseline scores

• Proportion of participants endorsing each response option of the FACIT GP5

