#### **10.3.7 Other Analyses**

Pharmacodynamic biomarker exploratory analyses and exploratory analyses of clinical outcomes assessments will be described in detail in the Statistical Analysis Plan finalized before database lock. OSR at 1 year and 2 years will be analyzed similarly to PFS. The population PK/ER and pharmacodynamic analyses may be presented separately from the main Clinical Study Report.

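### The 1- and 2-year survival rates are assigned a Brookmeyer-Crowley interval, which bounds a median time and cannot give limits for a survival probability

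*Combined protocol and SAP*

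**What the plan says.** Table 4-1 lists "OSR at 1 year and 2 years" as an exploratory endpoint for Parts 1, 2A and 2B. Table 10.3.1-1 defines the quantity: "OSR at a certain time point is defined as the proportion of subjects alive at that time point since the first dosing date".

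The method cell beside that definition calls for a Kaplan-Meier estimate and "corresponding 2-sided 95% CI using Brookmeyer and Crowley methodology (using log-log transformation) by treatment for each tumor type". The DOR and PFS rows of the same table carry identical text.

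Two other places bear on OSR:

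- Section 10.3.7: "OSR at 1 year and 2 years will be analyzed similarly to PFS".
- Section 10.3.1: "Details of the censoring scheme on time-to-event endpoints such as DOR, PFS, TTR, and OSR will be described in the Statistical Analysis Plan". This defers the censoring rules and does not mention the interval method.

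Neither document section names Greenwood's formula or any other pointwise interval for a survival probability.

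**The concern.** OSR at 1 year is a number between 0 and 1, and its confidence limits must be too. Brookmeyer-Crowley answers a different question. It fixes a survival level, usually 50%, and finds the times at which the curve is compatible with that level, so its output is an interval on the time axis.

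The row therefore names a method that cannot produce the interval it asks for. This is not a missing detail, since a method is stated and it does not fit the endpoint. A programmer following the cell literally would get one interval in months for the median, the same one for the 1-year and the 2-year rate. A programmer who noticed would have to substitute another method, and the analysis would then depart from the written plan.

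**Working it through.** The plan states no OSR value, interval or sample size, so there is no figure of its own to reproduce. The check is by definition, followed by an illustration.

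**Inputs from the documents.** Estimand: proportion alive at a fixed time (Table 10.3.1-1). Time points: 1 and 2 years (Table 4-1, Section 10.3.7). Level: 95%, two-sided, so z = 1.96. Stated method: Brookmeyer-Crowley, log-log.

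**The two procedures.** Let S(t) be the Kaplan-Meier estimate and V(t) = Σ d/[n(n − d)] the Greenwood sum over event times up to t.

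1. Brookmeyer-Crowley for the median is the set of times t for which |log(−log S(t)) − log(−log 0.5)| × |log S(t)| / √V(t) ≤ 1.96. The unknown is t, so the result is in months.
2. The pointwise log-log interval at a fixed time t₀ is S(t₀)^exp(±1.96 √V(t₀) / |log S(t₀)|). The unknown is the survival probability, so the result is a percentage.

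Both use Kaplan-Meier, Greenwood and the log-log scale. The first reads across the curve at a fixed height, and the second reads up and down at a fixed time. A time t belongs to the first set exactly when the second interval at t contains 50%.

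**Illustration.** Arm sizes are redacted, so these are assumptions: n = 20, 40 or 80; exponential survival with true median 8 or 12 months; censoring uniform on 18 to 40 months; one simulated data set per scenario.

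Worked case, n = 40, true median 12 months. Nobody is censored before 18 months, and S(12) = 23/40 = 0.575.

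- V(12) = 17/(40 × 23) = 0.01848, and √V = 0.1359.
- |log 0.575| = 0.5534, and 1.96 × 0.1359/0.5534 = 0.4814.
- exp(0.4814) = 1.618 and exp(−0.4814) = 0.618.
- Lower limit 0.575^1.618 = 0.408; upper limit 0.575^0.618 = 0.710.

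The 1-year OSR is 57.5% (95% CI 40.8% to 71.0%). Brookmeyer-Crowley on the same data gives a median of 15.6 months (95% CI 8.0 to 20.2 months). The two agree with each other: the 1-year interval contains 50% and 12 months lies inside 8.0 to 20.2, while the 2-year interval (13.8% to 42.2%) excludes 50% and 24 months lies outside.

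| n | True median (months) | Brookmeyer-Crowley 95% CI (months) | 1-year OSR (95% CI) | 2-year OSR (95% CI) |
|---|---|---|---|---|
| 20 | 8 | 2.7–12.0 | 30.0% (12.3–50.1) | 10.0% (1.7–27.2) |
| 20 | 12 | 4.0–18.0 | 45.0% (23.1–64.7) | 20.0% (6.2–39.3) |
| 40 | 8 | 5.3–13.5 | 47.5% (31.6–61.8) | 13.4% (4.2–27.7) |
| 40 | 12 | 8.0–20.2 | 57.5% (40.8–71.0) | 27.1% (13.8–42.2) |
| 80 | 8 | 6.1–10.7 | 37.5% (27.0–47.9) | 12.5% (6.2–21.1) |
| 80 | 12 | 9.2–16.0 | 52.5% (41.0–62.7) | 24.1% (15.3–34.1) |

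In every scenario the named method returned a single interval in months and no limits for either survival rate.

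**Does another passage supply the right method?** Section 10.3.7 sends OSR to PFS, and the PFS row names only Brookmeyer-Crowley. Section 10.3.1 defers censoring only. The ORR row, also a proportion, does receive an interval for a proportion (Clopper-Pearson).

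**The case against.** The best reply is that this is a labelling slip with little practical risk. The cell already specifies Kaplan-Meier and the log-log scale, the same estimator and scale as the correct interval. The text was probably copied from the DOR and PFS rows, and the authors may well have meant the pointwise log-log interval. An interval in months beside a percentage would be noticed at once. Section 10.3 also describes itself as a summary, with a Statistical Analysis Plan to be finalized before database lock. Section 10.3.7 says only that the approach is similar to PFS, which Kaplan-Meier estimation alone would satisfy. Finally, OSR is exploratory.

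Most of this stands as a matter of weight. A wrong published interval is unlikely, and the wording of Section 10.3.7 is loose enough that correcting the table cell would largely settle it. It does not change the substance: the method named is not one that yields the interval requested, and the only OSR detail expressly left to the later plan is the censoring scheme. Relying on a programmer to replace the stated method silently is a reason to correct the text now.

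**Conclusion.** The row is wrong as written: Brookmeyer-Crowley cannot give a confidence interval for survival at 1 or 2 years. That follows from the definitions and does not depend on the simulated figures, which only show the difference in units under assumed arm sizes and survival.

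The importance is low. OSR is exploratory and descriptive in Parts 1, 2A and 2B, and no sample size, alpha level, interim rule or safety boundary depends on it. One point adds a little weight: Part 2C has overall survival as a secondary endpoint, and Table 10.3.1-1 has no separate overall survival row, so the OSR row is the table's only survival specification.

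**What to change.** In the OSR row of Table 10.3.1-1, specify the Kaplan-Meier estimate at 1 and 2 years with a two-sided 95% pointwise confidence interval from Greenwood's variance with log-log transformation. Keep Brookmeyer-Crowley in the DOR and PFS rows, and add that it applies to the median. In Section 10.3.7, replace the reference to the PFS method with a reference to the corrected OSR row, and carry the same wording into the Statistical Analysis Plan.

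The cost is one table cell and one sentence, plus a clarifying word in two rows. Data collection, sample size and trial conduct are unaffected.
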